### **7.4.2.2 Dose Reductions/Escalations and Infusion Interruption**

There will be no dose escalations or reductions of nivolumab allowed. Subjects may be dosed no less than 12 days from the previous dose.

Nivolumab infusion can be interrupted and/or the IV infusion rate can be reduced. This information will be retrieved from CRF dosing pages.

The following will be summarized:

- Number of subjects with at least one infusion with iv rate reduced along with the reason of the rate reduction and number of infusions with IV rate reduction per subject
- Number of subjects with at least one dose infusion interrupted along with the reason for the interruptions and number of infusions interrupted per subject

A by subject listing of study drug administered will be provided. A batch listing number will be also provided.

### **7.4.3 Concomitant Medications**

Concomitant medications, defined as medications other than study medications which are taken at any time on-treatment (i.e. on or after the first day of study therapy and within 100 days following the last dose of study therapy), will be coded using the WHO Drug Dictionary.

The following summary tables will be provided:

- Concomitant medications (subjects with any concomitant medication, subjects by medication class and generic term)
- Immune modulating concomitant medication

A by-subject listing will accompany the tables.

## **7.5 Efficacy**

### **7.5.1 OS**

#### **7.5.1.1 Survival Analysis**

The OS curve will be estimated using the Kaplan-Meier (KM) product-limit method, along with the median and its 95% CI using Brookmeyer and Crowley method. Survival rates at different

time points (at 6, 12, 18, 24, and 36 months) will also be estimated using KM estimates from the OS curve. Associated two-sided 95% CIs will be calculated using the Greenwood formula. This analysis will be performed for all treated subjects and all subjects in Groups 1, 2, and 3.

The status of subjects who are censored in the OS Kaplan-Meier analysis will be tabulated for Group 1, 2, and 3, using following categories:

- on-study (on-treatment and not progressed, on-treatment progressed, in follow-up);
- off-study: (lost to follow-up, withdraw consent, etc.).

A by subject listing of overall survival will be produced.

#### **7.5.1.2 Subject Follow-up**

The currentness of follow-up for survival will be explored with the following K-M curve. The time between “the last known alive date” and the “Last Patient Last Visit Date” for alive subjects will be presented. Medians along with 95% CI using Brookmeyer and Crowley method will also be provided. The currentness of follow-up will be categorized into the following categories: 0 days, 1-3 months, 3-6 months, 6-9 months, 9-12 months and  $\geq 12$  months.

#### **7.5.1.3 Follow-up Therapy**

Subsequent therapies will be summarized and listed.

- Subsequent Therapy
  - Any subsequent therapy
  - Surgery
  - Radiotherapy
  - Subsequent systemic therapy classified by therapeutic class and generic name
- By Subject Listing of Subsequent Therapy

#### **7.5.1.4 Analysis of Survival by Tumor Response**

Survival by response category will be analyzed by treatment group using the landmark method. In the landmark method, a fixed time after the initiation of therapy is selected as a landmark for conducting the analysis of survival by response. Subjects still on study at the landmark time will be separated into two response categories according to whether they have responded before that time. This will assess whether survival from the landmark depends on the subject's response status at the landmark. Subjects who go off protocol (e.g. subjects who die) before the time of landmark will be excluded from the analysis.

The survival curves from Week 8, Month 4, Month 6, Month 8, Month 12, by response status, will be produced using the KM product-limit method for all treated subjects who are still at risk and all subjects in Groups 1, 2, and 3. Two-sided, 95% CIs for median OS will be computed.

[REDACTED]

[REDACTED]

[REDACTED]

[REDACTED]

[REDACTED]

[REDACTED]

[REDACTED]

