Archived Tumor Tissue or Recent Tumor Biopsy	X	One formalin-fixed paraffin embedded tumor tissue block, or 15 minimum FFPE unstained slides are to be submitted, if available. Submit a copy of the original pathology report along with the sample. Tissue samples from different biopsy procedures are to be submitted if available with each matching pathology report and biopsy date. Tissue sample from the metastatic tumor can be submitted if the primary tumor tissue is not available.

Table 5.1-2: On-Study Procedural Outline (CA209374)				
Procedure	Each Cycle Day 1	2nd Dose of Cycle	Q 8 wks from Day 1 Cycle 1	Notes
Safety Assessments				
Targeted assessments	X			Cycle 2 and beyond. Assessments within 48 hrs prior to dosing to include: Targeted physical exam, performance status and weight. Oxygen saturation by pulse oximetry at rest and after exertion for patients who complain of dyspnea or other respiratory symptoms
Adverse Events Assessment	Continuously assessed using NCI CTCAE v. 4.0.			
Concomitant Medications	X	X		
Laboratory Tests	X			Cycle 2 and beyond: (within 72 hrs prior to dosing) CBC w/differential, LFTs, BUN or serum urea, creatinine. TSH (reflex to free T3 and free T4 if abnormal result).
		X		LFTS only (within 72 hours prior to dosing)
Pregnancy Test	X			
Efficacy Assessments				
Radiographic Tumor Assessments			X	At Week 8 ( $\pm$ 1 week) and every 8 weeks $\pm$ 1 week thereafter, regardless of dosing schedule for the first 13 months then every 12 weeks $\pm$ 1 week until progression or treatment discontinuation whichever occurs later. Subjects with a history of brain metastasis perform surveillance CT/MRI approximately every 12 weeks, or sooner if clinically indicated.

Table 5.1-2: On-Study Procedural Outline (CA209374)				
Procedure	Each Cycle Day 1	2nd Dose of Cycle	Q 8 wks from Day 1 Cycle 1	Notes
Clinical Drug				
Administer Study Treatment	X	X		All subjects start treatment on C1D1 and continue treatment every 2 weeks for a maximum of 24 months or until confirmed progression, unacceptable toxicity, withdrawal of informed consent or discontinuation of the study by the Sponsor. Treatment for all subjects can continue beyond initial investigator-assessed progression. Drug administration is +/- 2 days but no less than 12 days from previous dose. Study drug infusion start and stop times will be recorded.
Other				

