Radiographic tumor assessments will be conducted at Week 8 ( $\pm 1$  week) and every 8 weeks ( $\pm 1$  week) for the first 13 months and then every 12 weeks ( $\pm 1$  week) until disease progression or treatment discontinuation whichever occurs later. Tumor assessments for all subjects should continue as per protocol even if dosing is interrupted. Tumor measurements should be made by the same investigator or radiologist for each assessment whenever possible. Changes in tumor measurements and tumor responses to guide ongoing study treatment decisions will be assessed by the investigator using RECIST 1.1 (see [Appendix 1](#) for details of RECIST 1.1).

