## 8 CONVENTIONS

The following conventions may be used for imputing partial dates for analyses requiring dates:

For missing and partial adverse event onset dates, imputation will be performed using the Adverse Event Domain Requirements Specification. Missing and partial Non-Study Medication Domain dates will be imputed using the derivation algorithm described in BMS Non-Study Medication Domain Requirements Specification.

For death dates, the following conventions will be used for imputing partial dates:

- If only the day of the month is missing, the 1st of the month will be used to replace the missing day. The imputed date will be compared to the last known alive date +1 day and the maximum will be considered as the death date.
- If the month or the year is missing, the death date will be imputed as the last known alive date + 1 day
- If the date is completely missing but the reason for death is present the death date will be imputed as the last known alive date + 1 day

For date of progression, the following conventions will be used for imputing partial dates:

- If only the day of the month is missing, the 1st of the month will be used to replace the missing day.

- If the day and month are missing or a date is completely missing, it will be considered as missing.
- \* In case, the date of death is present and complete, the imputed progression date will be compared to the date of death. The minimum of the imputed progression date and date of death will be considered as the date of progression.

The following conversion factors will be used to convert days to months or years: 1 month = 30.4375 days and 1 year = 365.25 days.

Duration (e.g. time from first diagnosis of NSCLC to first dosing date, duration response, and time to response) will be calculated as follows:

Duration = (Last date - first date + 1)

All statistical analyses will be carried out using SAS (Statistical Analysis System software, SAS Institute, North Carolina, USA) unless otherwise noted.

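### The Week 8 landmark for survival by response sits at the midpoint of the first scan window, so responder status at that landmark depends partly on scan timing (minor)

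*SAP*

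**What the plan says.** SAP 7.5.1.4 uses the landmark method, in which "a fixed time after the initiation of therapy is selected as a landmark". The classification rule is: "Subjects still on study at the landmark time will be separated into two response categories according to whether they have responded before that time". Subjects who go off protocol before the landmark, for example by dying, are excluded. The landmarks are listed as "The survival curves from Week 8, Month 4, Month 6, Month 8, Month 12, by response status". The curves are produced for all treated subjects still at risk and for Groups 1, 2 and 3, with 95% confidence intervals for median survival. The visible text plans no test and no decision rule.

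On scanning, Protocol 5.4.1 states "Radiographic tumor assessments will be conducted at Week 8", with a tolerance of ± 1 week. Assessments then follow every 8 weeks with the same tolerance for the first 13 months, and every 12 weeks after that. Table 5.1-2 heads the relevant column "Q 8 wks from Day 1 Cycle 1" and keeps the schedule fixed "regardless of dosing schedule for the first 13 months then every 12 weeks". Apart from the screening scan, nothing is scheduled before Week 8.

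SAP Section 8 gives the conversion "1 month = 30.4375 days and 1 year = 365.25 days".

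**The concern.** A landmark analysis is informative when subjects have had the same opportunity to be classified by the landmark. At Week 8 they have not. Some will have had their first scan. Others, equally compliant, will have it in the following week and go into the non-responder curve because nobody has yet looked.

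If response goes with longer survival, placing such subjects among the non-responders raises that curve and narrows the difference that the section sets out to assess. It also removes subjects from a responder group that may be small, particularly in Group 3, where about 25 subjects are planned.

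**Working it through.** The documents state no figure for this, so there is none to reproduce. The check is calendar arithmetic followed by a range for the one unknown.

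**Inputs**
- Landmark origin: start of therapy (SAP 7.5.1.4).
- Scan origin: Cycle 1 Day 1 (Protocol Table 5.1-2), which is the same day.
- Scan windows in the first 13 months: 56k ± 7 days, k = 1, 2, 3, ... (Protocol 5.4.1).
- Months to days: × 30.4375 (SAP Section 8).
- Rule: responded *before* the landmark (SAP 7.5.1.4).
- Distribution of scan dates within the window: not given.

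**Step 1. Where each landmark falls**

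| Landmark | Day | Last window closed before it | Inside a window? |
|---|---|---|---|
| Week 8 | 8 × 7 = 56 | none | Yes: days 49-63, at the midpoint |
| Month 4 | 4 × 30.4375 = 121.75 | Week 16, closes day 119 | No |
| Month 6 | 6 × 30.4375 = 182.6 | Week 24, closes day 175 | No |
| Month 8 | 8 × 30.4375 = 243.5 | Week 32, closes day 231 | No |
| Month 12 | 12 × 30.4375 = 365.25 | Week 48, closes day 343 | No |

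Only Week 8 is affected. Both clocks start at first dose, so numbering the first dose as day 0 or day 1 shifts both together and changes nothing.

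**Step 2. Who cannot be a Week 8 responder**

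The window holds 63 − 49 + 1 = 15 days. Scans on days 57-63 (7 days) come after the landmark. A scan on day 56 is not before it if the rule is read literally, which makes 8 days. This holds whatever the distribution of dates.

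**Step 3. Share of first-scan responders affected**

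Each row is an assumption about scan dates. The normal distributions are truncated to the window, with SD 2 to 3 days.

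| Scan dates | Day 56 not before | Day 56 counts as before |
|---|---|---|
| Uniform over the window | 8/15 = 53% | 7/15 = 47% |
| Centred on day 56 | 57-60% | 40-43% |
| Centred 3 days early | 11-22% | 4-13% |
| Centred 3 days late | 87-96% | 78-89% |
| Limits | 0% to 100% | 0% to 100% |

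**Step 4. What that does to the contrast**

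Let r be the true first-scan response proportion and m the share from Step 3. Responders then make up c = rm / (1 − r + rm) of the non-responder group. If timing within the window is unrelated to prognosis, the difference in survival probability at any time shrinks by the factor 1 − c. The visible text gives no r, so take 10-20% as an assumption:
- r = 0.10, m = 7/15: c = 0.0467 / 0.9467 = 5%.
- r = 0.20, m = 8/15: c = 0.1067 / 0.9067 = 12%.
- Wider range, r = 0.10 with m = 0.04 up to r = 0.20 with m = 0.96: c = 0.004 / 0.904 = 0.4% up to 0.192 / 0.992 = 19%.

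On these assumptions the dilution is modest. The loss of subjects from the responder curve, a fraction m of them, is the larger effect.

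**The case against.** Four points can be made for the plan.

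1. *A response documented after a landmark is meant to be a non-response at that landmark.* This is how the method avoids using later information, and it happens at all five landmarks, so calling these subjects misclassified goes too far. That stands as a point of wording. What remains is narrower: at Week 8 alone, some compliant subjects have had no on-study scan by the landmark, so the split reflects scheduling as well as response.

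2. *Little rests on this curve.* The primary and secondary objectives concern high-grade immune-mediated adverse events. Survival by response is a descriptive display with four other landmarks, each placed after a closed scan window. This stands and limits the severity.

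3. *Redacted blocks follow the visible text of SAP 7.5.1.4 and the secondary endpoints in SAP 4.2.* A response-date or window convention could be in either place. This cannot be excluded. The visible rule contains none.

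4. *Week 8 may mean the Week 8 assessment rather than day 56.* It is the only landmark given in weeks, and it matches the scan label. The SAP's own description of a landmark as "a fixed time after the initiation of therapy is selected as a landmark" weighs against this, but it is a reason to ask for clarification.

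Two stronger readings are tempting. A reader might infer that about half of first-scan responders will land in the wrong curve. That needs scan dates spread symmetrically around day 56, and the documents give only the window. A head count would also need a first-scan response rate, which the visible text does not supply. A reader might also infer that the Week 8 curves cannot be interpreted. That does not follow: every subject counted as a Week 8 responder must still have a documented response, so the responder curve is depleted but not contaminated.

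**Conclusion.** The scheduling conflict is certain on the visible text. Week 8 is the exact centre of the first scan window, both clocks start at first dose, and the rule is "separated into two response categories according to whether they have responded before that time". Responder status at this landmark therefore depends partly on scan timing, and the contrast is likely diluted, provided that response is associated with longer survival.

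The size is not known. The affected share of first-scan responders is 47-53% under uniform scan dates, and the other assumed patterns tried take it from about 4% to 96%. The share would be 0% if every first scan fell before day 56 and 100% if every one fell after it.

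Severity is minor. The primary safety result and the later landmarks are untouched, and a convention in the redacted text would settle the matter.

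**What to change.** In SAP 7.5.1.4, move the first landmark to after the first scan window closes, and leave the other four landmarks as they are. Either wording works:
- day 64 or later, keeping *before*; or
- Week 9 (day 63), with *on or before* replacing *before*.

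Changing Week 8 to Week 9 alone is not quite enough. A compliant scan on day 63 is not before day 63, so 1/15 = 7% of first-scan responders would still be excluded under uniform dates. With either wording above, no in-window first-scan responder is excluded. If a window convention already exists in the redacted text, a cross-reference in this section would serve.

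The cost is a wording change, with no effect on data collection, sample size or patient care. The one downside is that subjects who die or go off protocol between Week 8 and the new landmark (64 − 56 = 8 days at the earliest *before* option) drop out of this one landmark.

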## **7.6 Safety**

### **7.6.1 Primary Analyses**

The number and percentage of subjects who report high grade (Grade 3-4 and Grade 5) IMAEs will be summarized for all treated subjects. High grade (Grade 3-4 and Grade 5) IMAEs will be tabulated using worst grade per NCI CTCAE v4.0 criteria by system organ class and Medical Dictionary for Regulatory Affairs (MedDRA) preferred term.

### **7.6.2 Secondary Analyses**

Additional descriptive statistics will include median values using the Kaplan-Meier (KM) product-limit method with 95% CI using Brookmeyer and Crowley of time to onset and time to resolution of IMAEs, and will be presented for all treated subjects in Groups 1, 2, and 3. Time to onset is calculated from first dosing date to the event onset date. If a subject never experienced the given AE, the subject will be censored at the last contact date. Time to resolution is calculated from the AE onset date to AE end date. If an AE is ongoing at the time of analysis, the time to resolution will be censored at the last contact date.

Management of high-grade (CTCAE v4.0 Grade 3-4 and Grade 5) IMAEs will be characterized by measuring percentage of subjects who received immune modulating medication (or hormonal replacement therapy), percentage of subjects who received  $\geq 40$  mg prednisone equivalents, and total duration of all immune modulating medications given for the event, in all treated subjects who have experience high-grade (CTCAE v4.0 Grade 3-4 and Grade 5) IMAEs and all subjects in Groups 1, 2, and 3.

### **7.6.3 Deaths**

See Section 7.6.1 of Core Safety SAP

### **7.6.4 Serious Adverse Events**

See Section 7.6.2 of Core Safety SAP

### **7.6.5 Adverse Events Leading to Discontinuation of Study Therapy**

See Section 7.6.3 of Core Safety SAP

### **7.6.6 Adverse Events Leading to Dose Delay of Study Therapy**

See Section 7.6.4 of Core Safety SAP

### **7.6.7 Adverse Events**

See Section 7.6.5 of Core Safety SAP

### **7.6.8 Immune Mediated Adverse Events**

IMAEs are specific events occurring within 100 days of the last dose of study drug (which includes pneumonitis, diarrhea/colitis, hepatitis, nephritis/renal dysfunction, rash, and endocrine abnormalities [adrenal insufficiency, hypothyroidism/thyroiditis, hyperthyroidism, diabetes mellitus, and hypophysitis]), regardless of causality, for which subjects received immunosuppressive medication for treatment of the event. The exception to the immunosuppressive medication criteria for IMAEs is endocrine events (hypothyroidism/thyroiditis, hyperthyroidism, hypophysitis, diabetes mellitus, adrenal insufficiency), which are included regardless of treatment since these events are often managed without immunosuppression.

Unless otherwise specified, analyses will be performed by IMAE category on events where immune modulating medication was initiated. Analyses may also be repeated by categories of endocrine events.

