### **6.2.2 Adverse Events of Interest**

IMAEs are specific events occurring within 100 days of the last dose of study drug (which includes pneumonitis, diarrhea/colitis, hepatitis, nephritis/renal dysfunction, rash, and endocrine abnormalities [adrenal insufficiency, hypothyroidism/thyroiditis, hyperthyroidism, diabetes mellitus, and hypophysitis]), regardless of causality, for which subjects received immunosuppressive medication for treatment of the event. The exception to the immunosuppressive medication criteria for IMAEs is endocrine events

(hypothyroidism/thyroiditis, hyperthyroidism, hypophysitis, diabetes mellitus, adrenal insufficiency), which are included regardless of treatment since these events are often managed without immunosuppression.

Per FDA guidance, IMAE analyses included events, regardless of causality, occurring within 100 days of the last dose. These analyses are limited to subjects who received immunosuppressive medication for treatment of the event, with the exception of endocrine events (hypothyroidism/thyroiditis, hyperthyroidism, hypophysitis, diabetes mellitus, adrenal insufficiency), which were included in the analysis regardless of treatment since these events are often managed without immunosuppression.

Table 6.2.2-1 provides a summary of the IMAEs category and their respective PTs.

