#### 4 ENDPOINTS

##### 4.1 Primary Endpoint(s)

The primary objective of the study will be assessed by measuring the incidence for high grade (Grade 3-4 and Grade 5) IMAEs.

The IMAEs are the following: skin, endocrinopathy, gastrointestinal, hepatic, renal, pulmonary, and neurologic adverse events.

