### **7.6.8.1 Incidence of IMAE**

IMAEs will be summarized for each category:

- Overall summary of any IMAEs by worst CTC grade presented by Category/PT (any grade, grade 3-4, grade 5)
- Overall summary of any serious IMAEs by worst CTC grade presented by Category /PT (any grade, grade 3-4, grade 5)
- Overall summary of any IMAEs leading to discontinuation by worst CTC grade presented by Category/PT (any grade, grade 3-4, grade 5)
- Overall summary of any IMAEs leading to drug delay by worst CTC grade presented by Category/PT (any grade, grade 3-4, grade 5)
- Overall summary of drug-related IMAEs by worst CTC grade presented by Category/PT (any grade, grade 3-4, grade 5)
- Overall summary of drug-related IMAEs leading to discontinuation by worst CTC grade presented by Category/PT (any grade, grade 3-4, grade 5)
- Overall summary of any IMAEs by worst CTC grade presented by Category/PT (grade 1, 2, 3, 4, 5, unknown)
- Overall summary of any serious IMAEs by worst CTC grade presented by Category/PT (grade 1, 2, 3, 4, 5, unknown)
- Overall summary of any IMAEs leading to discontinuation by worst CTC grade presented by Category/PT (grade 1, 2, 3, 4, 5, unknown)
- Overall summary of any IMAEs leading to drug delay by worst CTC grade presented by Category/PT (grade 1, 2, 3, 4, 5, unknown)

The analyses will be conducted using the 100-day safety window.

By-subject IMAE listing will be provided.

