### **7.6.8.2 Time-to onset of IMAE**

Time-to onset of the following specific events will be summarized for each category of IMAEs:

- Time-to onset of any grade IMAE
- Time-to onset of grade 3 to 5 IMAE
- Time-to onset of any grade IMAE where immune modulating medication was initiated
- Time-to onset of grade 3 to 5 IMAE where immune modulating medication was initiated

The following summary statistics will be reported for treated subjects who experienced at least one immune-mediated adverse event from the category: median, min and max. Median time to onset along with 95% confidence interval using the Kaplan-Meier technique is also reported for all treated subjects. If the subject did not experience a IMAE in the category, time-to onset will be censored at the maximum follow-up time of all subjects in their respective treatment group (i.e. for subjects without an event, follow-up time is defined from first dosing date up to last dosing date +100 days if subjects are off treatment and followed for at least 100 days, otherwise it is defined up to the last known alive date).

See time-to onset definition subsection of [Appendix 1](#) for additional details. The analyses will be conducted using the 100-day safety window.

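### SAP 7.6.8 counts endocrine IMAEs whatever their treatment, but its default analysis rule has no endocrine exception, so read literally the 7.6.8.1 incidence tables omit endocrine IMAEs not given immune modulating medication

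*SAP*

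**What the plan says.** The first paragraph of SAP 7.6.8 defines an IMAE. An event in a listed category, within 100 days of the last dose, counts if the subject was given immunosuppressive medication for it. One group is exempt: "The exception to the immunosuppressive medication criteria for IMAEs is endocrine events". The five named endocrine categories are events "which are included regardless of treatment since these events are often managed without immunosuppression".

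Protocol 6.2.2 has the same definition. It also says that the exemption governs the analysis and not only the label, describing endocrine events as ones "which were included in the analysis regardless of treatment since these events are often managed without immunosuppression".

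The second paragraph of SAP 7.6.8 then gives a general rule for the IMAE analyses: "Unless otherwise specified, analyses will be performed by IMAE category on events where immune modulating medication was initiated". The only mention of endocrine events in that paragraph is "Analyses may also be repeated by categories of endocrine events".

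SAP 7.6.8.1 lists ten incidence summaries of IMAEs, by category, preferred term and worst grade. It sets the 100-day window and says nothing about medication. SAP 7.6.1, the primary analysis, asks for the number and percentage of treated subjects with a high-grade IMAE and states no medication condition. SAP 4.1 names endocrinopathy as part of the primary endpoint: "The IMAEs are the following: skin, endocrinopathy, gastrointestinal, hepatic, renal, pulmonary, and neurologic adverse events".

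**The concern.** The definition and the default cannot both govern the same table. A high-grade endocrine event treated only with hormone replacement is an IMAE under the first paragraph of 7.6.8 and falls outside the analysis set under the second. Non-endocrine IMAEs already need immunosuppressive treatment to meet the definition, so the default has little effect on them. Nearly all of its effect falls on the events that the definition exempts.

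Two consequences follow. First, the detailed incidence tables would understate endocrine toxicity in a safety trial whose primary endpoint names it; the error can only lower the count. Second, the high-grade count behind 7.6.8.1 could differ from the count in 7.6.1, with nothing in the SAP to explain why.

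**Working it through.** The contradiction is in the text. Arithmetic bears only on what would follow if the default reached the primary count.

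**1. Does anything lift the default for incidence?**
- SAP 7.6.8.1 has ten summaries, and none changes the event set.
- The sentence on repeating analyses by endocrine category is optional. It concerns grouping, not treatment, so it does not restore the omitted events.
- SAP 4.2 and 7.6.2 name hormone replacement separately from immune modulating medication, so an event treated with hormones alone does not clearly satisfy the default.
- The rule is not standard wording in this SAP. The matching openings of 7.6.10 (select AEs) and 7.6.11 (other events of special interest) say that analyses are by category and set no medication condition.

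**2. Does the default fit the rest of 7.6.8?**
- SAP 7.6.8.2 lists time to onset of Grade 3 to 5 IMAEs and, as a further item, "Time-to onset of grade 3 to 5 IMAE where immune modulating medication was initiated". Under the default these are the same set.
- SAP 7.6.8.4 reports, by IMAE category, the percentage of subjects with an event who received immune modulating medication. (Its text refers to other events of special interest, but its heading and opening line refer to IMAEs.) If every analysed event already had such medication, the answer is 100% by construction. Endocrine events are where the figure would be informative.

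So the default conflicts with the definition before it and with two of the subsections after it.

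**3. The protocol's own figures.** Inputs from protocol 8.1 and Table 8.1-1: n = 150, assumed Grade 3-5 IMAE rate 13%, criterion that the 95% interval lies wholly below 20%, cut-off 20 of 150.

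Exact (Clopper-Pearson) upper limit for x events = 0.975 quantile of Beta(x + 1, 150 − x).
- x = 20 (20/150 = 13.33%): 19.84%, below 20%. This is the table row labelled 13.0%.
- x = 21 (21/150 = 14.0%): 20.60%, not below 20%.

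Probability of meeting the criterion = P(X ≤ 20), X ~ Binomial(150, p).
- p = 13%: 60.7% (protocol: 61%).
- p = 11.5%: 80.0% (protocol: 80%).

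The plan's figures reproduce. One subject is 1/150 = 0.67 percentage points, and the criterion turns between 20 and 21.

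**4. Conditional illustration.** Suppose the default were carried into the primary count. Let s be the share of subjects with a high-grade IMAE whose only such event is endocrine and without immune modulating medication. The documents give no value for s; the range of 5% to 30% is an assumption. The counted rate becomes p × (1 − s), and the probability is P(X ≤ 20) at that rate.

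| s (assumed) | True 13%: counted rate | Chance of meeting 20% criterion | True 20%: counted rate | Chance of meeting 20% criterion |
|---|---|---|---|---|
| 0 | 13.0% | 60.7% | 20% | 2.2% |
| 5% | 12.35% | 69.6% | 19% | 4.4% |
| 10% | 11.7% | 77.8% | 18% | 8.0% |
| 20% | 10.4% | 90.2% | 16% | 22.1% |
| 30% | 9.1% | 96.8% | 14% | 46.4% |

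The table shows the direction and sensitivity of the error under that reading. It does not estimate an effect in this trial.

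**The case against.** The strongest reply is that the primary analysis is untouched. SAP 7.6.1 is a separate section with no medication condition, and the 20% criterion stands in protocol 8.1, not in the 7.6.8.1 tables, which plan no confidence interval and no comparison with 20%. This stands. A reader might infer that the plan biases the primary result towards meeting the 20% limit, but the documents do not say that the default applies to 7.6.1. What remains is that 7.6.1 has no IMAE definition of its own. The SAP's definition sits in 7.6.8, next to the conflicting sentence, and Appendix 1 points to a sponsor-held term list. A programmer has to decide.

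A second reply is that the context shows unqualified IMAE to mean the full definition. SAP 7.6.8.2 lists analyses with and without the medication condition, and 7.6.8.3 states a separate restriction for resolution where medication was started. This also stands: a reader might infer that the onset and resolution tables lose endocrine events too, but those sections are reasonably read as specifying otherwise. It suggests that the default sentence is a drafting slip. It does not correct the sentence for 7.6.8.1, where nothing else is specified.

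A third reply is that endocrine toxicity appears elsewhere. The select AE tables in 7.6.10 allow for endocrine subcategories and carry no default medication condition, and a by-subject IMAE listing is planned. This is only a partial answer. Select AEs are a separate grouping whose terms are not shown, and their incidence tables use a 30-day window, with only some repeated at 100 days. A listing is not an incidence table.

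**Conclusion.** The inconsistency is real and should be fixed. Read literally, the 7.6.8.1 incidence tables leave out endocrine IMAEs without immune modulating medication, contrary to protocol 6.2.2 and to the SAP's own definition. They would then understate high-grade endocrine toxicity and could disagree with the 7.6.1 count.

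Only part of the endocrine category is lost: events given corticosteroids as immune modulating medication, for example, stay in. The number affected is unknown. The primary conclusion is at risk only if the 7.6.8 default is carried into 7.6.1, which the SAP does not direct. In that case a single subject at the 20/21 boundary could change it, and the range in step 4 rests on an assumed share. Because the primary section is not expressly restricted, this is a correction to make before analysis and not a fault in the primary analysis itself.

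**What to change.** - Reword the default sentence in SAP 7.6.8 so that, unless an analysis says otherwise, the event set by category is non-endocrine events for which immune modulating medication was started, plus all endocrine events whatever their treatment.
- State that SAP 7.6.1 and 7.6.8.1 both use this event set.
- Apply the restriction to medication-treated events only in analyses listed as such, as 7.6.8.2 already does.

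The cost is one reworded sentence and one added statement in the SAP, with no new data. The tabulated endocrine IMAE counts may be slightly higher than under the literal default.
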